#### 9.3.2.1 Primary outcomes

- Obesity
- Smoking
- Alcohol consumption
- Abnormal renal function
- Bleeding history or predisposition
- Renal function (estimated GFR)
- Serum Creatinine
- Abnormal liver function

#### 9.3.2.2 Secondary outcomes

- Duration of atrial fibrillation
- History of adherence
- History/duration of hypertension
- Uncontrolled Hypertension (for HAS-BLED)
- History/duration of CHF
- Prior TIA
- Diabetes
- Hyperlipidemia
- HAS-BLED Score
- Use of antiplatelets or NSAIDs (needed for HAS-BLED)

**Table 1 Outcome definitions**

Outcome	Definition	Present	Categories if present
Primary			
Obesity	Calculated BMI >30 or recorded "obesity"	Y/N	Obese, not-obese based on note of obesity or recorded BMI>30.
Smoking	Any note on smoking	Y/N	Current & past combined and nonsmoker & not noted combined.
Alcohol consumption	Any note on alcohol use	Y/N	Alcohol use (any); No use
Abnormal renal function	Any note of: Dialysis, renal transplant Serum Creatinine >1.3 mg/dL	Y/N	
Bleeding history or predisposition	Any note of: Major bleeding requiring hospitalization or blood transfusion or causing a decrease in hemoglobin level of > 2 g/L	Y/N	
Renal function	Estimated GFR closest to index dispensing	Y/N	The value
Serum Creatinine	Closest to the index date	Y/N	The value
Abnormal liver function	Any note of: Liver disease, cirrhosis, Active hepatitis C Active hepatitis B Active hepatitis A AST/ALT >3X upper limit of normal Absence of any note would be considered as absence of the disease	Y/N	

[figure not shown]
Table 1 (cont'd) Outcome definitions

[figure not shown]
Outcome	Definition	Present	Categories if present
Secondary			
Duration of atrial fibrillation	Years/months prior to initiation of dabigatran/warfarin	Y/N	Number of months prior to index date for the earliest note
History of adherence	Any note of patient adherence/lack thereof in EMR	Y/N	Non-adherent Adherent
History/duration of hypertension	Any note of: Hypertension SBP >120 mmHg Hypertension drugs	Y/N	Number of months prior to index date for the earliest date
Uncontrolled Hypertension (for HASBLED)	SBP >160 mmHg using the most recent information prior to index date	Y/N	
History/duration of CHF	Any note of: CHF	Y/N	Number of months prior to index date for the earliest note
Prior TIA	Any note of TIA	Y/N	Also, number of months prior to index date if noted
Diabetes	Any note of: Diabetes Absence of any note of diabetes will be considered as absence of the disease	Y/N	
Hyperlipidemia	Any note of; Hyperlipidemia, dyslipidemia, LDL>130 mg/dl		
HAS Bled Score	As recorded (if recorded) or calculated from EMR data. [REDACTED]	Recorded/ calculated /none	The value
Use of antiplatelets or NSAIDs (needed for HASBLED)	Use of aspirin, clopidogrel, prasugrel, ticagrelor or NSADs (within 1 month or on the index date)	Y/N	
INR	Closest to the index date	Y/N	The value

[figure not shown]

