## 7. RATIONALE AND BACKGROUND

A number of new oral anticoagulants are being developed and marketed to replace vitamin K antagonists, one of the most important drugs in modern medicine. [P11-11875] Unlike vitamin K antagonists, these new drugs do not require dose titration involving intensive therapeutic monitoring of prothrombin time to achieve target anticoagulation within a narrow therapeutic range. In Phase III studies, these drugs were found to be therapeutically advantageous or non-inferior over warfarin. In the coming years, as many as six new anticoagulants could be on the market and a lack of valid comparative evidence will hinder prescriber and payor decision-making.

Pharmacoepidemiologic studies based on large administrative claims databases are increasingly utilized for that purpose; however, these data are collected for reasons unrelated to research, and as a result, might not contain sufficient information on important confounders, such as body mass index, smoking, family history, or alcohol consumption, leading to residual confounding. Several approaches have been proposed to address the issue of unmeasured confounding, and internal validation studies, based on additional data obtained for a subset of participants in the main study population is one of them. Such studies offer specific advantages since they are more representative of the main study population and allow application of methods that do not require assumptions about the direction of confounding. [R13-2768]

This protocol is for a validation study conducted within a cohort of patients initiating dabigatran or warfarin during October 2010 – December 2014 time period and matched on propensity score (PS). The study will involve targeted data ascertainment from linked patients for enhanced covariate assessment via extraction from electronic medical records using existing electronic data including pre-defined variables, with the goal of describing the presence of covariates not typically present or insufficiently measured in claims data in dabigatran users as compared to users of warfarin and assessing the potential for confounding in the comparative safety research that will be undertaken in other phases of the study program.

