**Table 9** **EMR clinical characteristics in matched dabigatran and warfarin initiators**

EMR clinical characteristic	Dabigatran initiators	Warfarin initiators
	N=	N=
[REDACTED]		
Smoking		
Alcohol consumption		
Obesity		
...		

[figure not shown]
Note: anticoagulant initiation [REDACTED] are based on claims data

We will seek to define variables derived from the EMR in a manner that reduces missingness. Accordingly, most variables will be defined as presence or non-presence in the EMR, which we will take as a proxy of being medically-recognized. For example, if smoking is noted in the medical record, it will be recorded as present, if it is not present, it will be assumed that the patient does not smoke. We will also evaluate the patterns of missing data in the EMR clinical characteristics.

Objective 2: Prediction Rule

[figure not shown]
Within the EMR linked subpopulation, a prediction model will be developed [REDACTED] with particular focus on covariates that are found to represent potentially important unmeasured confounding in the primary analysis. Specifically, a logistic regression model (potentially a multinomial logistic regression, depending on the number of categories for the EMR characteristic) will be estimated [REDACTED] that uses the EMR covariate as the model outcome and all available claims-based covariates as predictors. [REDACTED]

For [REDACTED] continuous EMR-based characteristic, a linear regression model will be estimated. Coefficients from these models will be reported as well as prediction accuracy, defined by the R2 statistic.

*Objective 3: Potential Unmeasured Confounding Assessment*

To assess the potential for confounding, we will conduct a series of logistic regression analyses that predict exposure (dabigatran versus warfarin) from covariates.

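### Table 1 pools current with past smokers and keeps body mass only as obese or not; this can mask imbalance within a category, and supplementary smoking-status and BMI rows would be a cheap improvement.

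*Combined protocol and SAP*

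**What the plan says.** Section 7 justifies the study by saying that claims may lack information on important confounders, "such as body mass index, smoking, family history, or alcohol consumption, leading to residual confounding".

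Section 9.3.2.1 lists obesity, smoking and alcohol consumption as primary outcomes. Table 1 gives each two levels:

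- Smoking: "Current & past combined and nonsmoker & not noted combined".
- Body mass: "Obese, not-obese based on note of obesity or recorded BMI>30".
- Alcohol: "Alcohol use (any); No use".

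The same table retains the measured value for other characteristics. Renal function is the "Estimated GFR closest to index dispensing", with its value kept, and serum creatinine and INR are treated the same way.

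Section 9.7.1 explains the general approach: "We will seek to define variables derived from the EMR in a manner that reduces missingness", so that "most variables will be defined as presence or non-presence in the EMR". For Objective 2 it provides logistic models, "potentially a multinomial logistic regression, depending on the number of categories for the EMR characteristic", and linear models for continuous characteristics. Objective 3 uses logistic regressions of drug choice on covariates.

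**The concern.** The EMR subset exists to add detail that claims lack, and section 9.12 sets the aim as judging the magnitude of potential confounding. For smoking and body mass, the coding gives up part of that detail before balance is assessed.

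The stated reason, fewer missing values, accounts for merging patients with no smoking note into nonsmokers. It does not account for pooling current with past smokers where the record tells them apart. Nor does it account for setting aside a BMI value that must be in hand wherever the cut at 30 is applied.

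If current and past smoking carry different risks, a null difference in ever-smoking does not establish that smoking is balanced. A single cut at 30 likewise puts low and normal weight in one group and all degrees of obesity in the other. Section 9.9 says that associations with clinical outcomes are not assessed, so nothing later in this study would reveal an imbalance hidden at this step.

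**Working it through.** **Size of the linked subset.** Section 9.5 gives about 20,000 matched initiators per group and 5.5% linkage: 20,000 × 0.055 = 1,100 per group, as stated there. The abstract's 15,000 gives 15,000 × 0.055 = 825. Both are used below.

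**Assumptions.** The visible text gives no distribution of smoking or BMI by drug and no balance threshold. All prevalences, BMI parameters and relative risks below are assumed.

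**Smoking, full offset.** Dabigatran: 8% current, 32% past. Warfarin: 14% current, 26% past.

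- As coded: 8 + 32 = 40% versus 14 + 26 = 40%, difference 0.
- Current smoking, standardised difference: 0.06 / √[(0.08×0.92 + 0.14×0.86)/2] = 0.06 / √0.097 = 0.19.
- Standard error at 1,100 per group: √[(0.08×0.92 + 0.14×0.86)/1,100] = 0.0133, so the difference is 0.06/0.0133 ≈ 4.5 SE. At 825 the SE is 0.0153, giving about 3.9 SE.

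**Smoking, milder offset.** Current 10% versus 15%, past 35% versus 30%. Ever-smoking is 45% in both groups. The standardised differences are −0.15 (current) and +0.11 (past). Power to see the current-smoking difference at two-sided 5% is 94% with 1,100 per group and 87% with 825.

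**Smoking, partial or no offset.** Keep current at 8% versus 14%.

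| Past smoking | Ever-smoking as coded | Difference in SE at 1,100 |
|---|---|---|
| 32% v 26% | 40% v 40% | 0 |
| 32% v 29% | 40% v 43% | 0.03/0.0210 = 1.4 |
| 30% v 30% | 38% v 44% | 0.06/0.0209 = 2.9 |

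The binary row weakens the signal as the offset grows and loses it only when the offset is exact.

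**Effect on an outcome comparison.** Bias factor = [1 + Σp_D(RR−1)] / [1 + Σp_W(RR−1)], where p_D and p_W are the prevalences on dabigatran and warfarin. For the full-offset example:

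- RR 1.5 current, 1.1 past: (1 + 0.040 + 0.032)/(1 + 0.070 + 0.026) = 1.072/1.096 = 0.98.
- RR 3 current, 1.2 past: (1 + 0.160 + 0.064)/(1 + 0.280 + 0.052) = 1.224/1.332 = 0.92.

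**BMI, normal distributions.**

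- Mean 30 in both groups, SD 5 versus 7: P(BMI>30) = 50% in both. P(BMI<20) = Φ(−10/5) = 2.3% versus Φ(−10/7) = 7.7%. The binary row misses this.
- Mean 30 versus 29, SD 6 in both: P(BMI>30) = 50% versus 1 − Φ(1/6) = 43.4%, about 3.1 SE at 1,100. The binary row shows this.

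**The case against.** **The coding is deliberate.** Besides the missingness argument, section 9.3.2 says that Table 1 reflects what is likely to be available in the EMR. A smoking note without timing can be classed as ever-smoker but not as current or past, so pooling does avoid some unclassifiable patients. This stands as a reason to keep the binary row. It does not argue against an extra row for patients whose status is recorded.

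**Low-prevalence strata are discounted.** Section 9.5 holds that characteristics below 10% have progressively less capacity to confound and need no validation. The BMI tail above (2.3% versus 7.7%) lies below that line, and current smoking (8% versus 14%) straddles it. This weakens the case for the BMI tails. It weakens the smoking case less, since the milder example lies at 10% and 15%.

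**The examples need particular numbers.** Complete cancellation needs an exact offset, and the BMI example needs equal means with unequal spread. Nothing in the documents suggests either in a propensity-matched cohort. That is correct, and it limits the claim to what the coding could hide.

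**Blacked-out text.** Parts of section 9.7.1 are not visible, and Table 9 is only an example, so a finer analysis may be planned there. The visible Table 1 definitions nevertheless fix two levels.

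**Alcohol.** A reader might extend the point to alcohol, where heavy use could be hidden within any use. Nothing visible shows that the EMR records quantity or severity, so the documents do not support more than a conditional suggestion.

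**Conclusion.** This is a worthwhile, inexpensive improvement rather than a flaw that undermines the study. For smoking and body mass, two-level coding sets aside information that the rationale says is wanted and that is at least partly in hand, and the stated missingness reason covers only part of the loss.

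The size cannot be fixed from the documents. Under the assumed figures, a current-smoking difference of about 0.15 to 0.19 standardised units can sit behind a zero difference in ever-smoking, in a sample able to detect it. The implied bias factors for an outcome comparison are modest, 0.92 to 0.98 in the full-offset example.

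Two stronger readings are tempting and not supported. One is that Objective 3 will report balance where none exists; that needs distributions by drug which the documents do not give. The other is that differences in body mass cannot be seen at a cut of 30. An ordinary mean shift would be seen; only differences in spread or tails are lost. True cancellation applies to smoking alone.

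**What to change.** Keep the binary rows as the main coding. Add to Tables 1 and 9, as supplementary rows where recorded:

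- smoking as current / past / ever with timing unknown / never or not noted;
- the BMI value closest to the index date, with mean, SD, number available, and categories that include the low end.

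Carry both into Objective 2, using the multinomial and linear models that section 9.7.1 already provides, and into the Objective 3 logistic models. Grade alcohol only if the EMR fields allow it. Section 9.11.2 has the data holder evaluate EMR balance, so the definitions should be agreed before that work starts.

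The cost is a few extra table rows and models. BMI or smoking timing will be missing for some patients, which is why the binary rows stay and the number available should be shown. The extra rows leave never-smokers and patients with no note merged, so misclassification from unrecorded smoking remains.

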Population:	
Patients from an US health insurance database (electronic medical records) with a recorded diagnosis of atrial fibrillation without evidence of valvular etiology and at risk for stroke who initiate dabigatran or warfarin between October 2010 and December 2014 (This date range corresponds to the available matched cohort date range).
 
Inclusion criteria:
 
 
• A recorded diagnosis of atrial fibrillation.
 
• Initiation of anticoagulant medication (dabigatran or warfarin).
 
• At least 18 years of age on the date of anticoagulant initiation.
 
• CHA2DS2-VASc score ≥ 1
 
• Presence of electronic medical records (for the EMR-based subset)
 
 
Exclusion criteria:
 
 
• Patients with missing or ambiguous age or sex information.
 
• Patients with evidence of valvular disease.
 
• Patients with less than 12 months enrolment preceding the date of anticoagulant initiation.
 
• Patients with a dispensing of any oral anticoagulant during the 12 months preceding the date of anticoagulant initiation
 
• Patients with a nursing home stay during baseline
 
• Unmatched dabigatran/warfarin initiators
 
		

Name of company: Boehringer Ingelheim			
Name of finished medicinal product: Pradaxa® (Dabigatran etexilate), or warfarin			
Name of active ingredient: Dabigatran etexilate or warfarin			
Protocol date: 02 November 2016	Study number: 1160.219	Version/Revision: 1.0	Version/Revision date:

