#### 9.3.2 Outcomes

EMR-based clinical characteristics that are typically used as covariates will be treated as outcomes in this validation study. Unless otherwise noted, all of these outcomes will have an indicator for being recorded in EMR (Present, Y/N). Index date is the date of dabigatran or

warfarin initiation. All characteristics will be assessed prior and including the medication initiation date (index date). The characteristics presented in [Table 1](#) reflect likely availability in the EMR.

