**Table 8 Association between claims-based covariates and EMR linkage.**

Claims-based covariate	Dabigatran initiators		Warfarin initiators	
	N=		N=	
	Linked	Not linked	Linked	Not linked
Proportion (N)				
Age				
Age category 18-35				
Age category 36-64				
Age category 65-74				
Age category 75+				
Sex				
...				

*Objective 1: Descriptive*

The analyses for this objective will occur within the subpopulation of individuals with linked EMR data and will focus on describing the EMR-based clinical characteristics for the dabigatran and warfarin initiators. This table will provide an evaluation of the association between the EMR clinical characteristics and initiation of dabigatran or warfarin. [REDACTED]

The prevalence of each category for categorical characteristics and the mean and standard deviation for continuous characteristics will be calculated (as shown in the example [Table 9](#)). This analysis will aid in identifying EMR characteristics that are unbalanced across exposure groups and are therefore potential unmeasured confounders after PS matching.

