## **9.11 SUBJECTS**

### **9.11.1 Study group**

The main cohort will consist of patients with NVAf at risk for stroke initiating warfarin and dabigatran, from October 2010 through December 2014.

Inclusion criteria:

- Initiation of an oral anticoagulant is defined by a dispensing of an anticoagulant medication (warfarin or dabigatran) in the source data, with no dispensing of any oral anticoagulant in the prior 12 months. The date of that dispensing will be defined as the index date for that initiation.
- At least one ICD-9 diagnosis code of 427.31 (atrial fibrillation) at any time prior to and including the index date
- At least 12 months (365 days) continuous enrollment, defined as  $\leq 32$  days enrollment gap using enrollment and disenrollment dates, preceding the index date
- 18 years of age and older at index date
- CHA2DS2-VASc score  $\geq 1$

Exclusion criteria:

- Patients with a nursing home stay during baseline
- Patients with missing or ambiguous age or sex information.
- Patients with a dispensing of any oral anticoagulant during the 12 months preceding and including the index date
- Patients with documented evidence of valvular disease defined as at least 1 inpatient or outpatient ICD-9 Dx code of [\[R11-4334\]](#)  
394.x (diseases of mitral valve)  
395.x (diseases of aortic valve)  
396.x (diseases of mitral and aortic valve)  
397.x (diseases of other endocardial structures)  
398.9x (other and unspecified rheumatic heart diseases)  
V42.2 (heart valve replaced by transplant)  
V43.3 (heart valve replaced by a mechanical device/prosthesis)  
OR  
ICD-9 procedure code 35.1x (open heart valvuloplasty without replacement), 35.2x (replacement of heart valve) [\[R03-1232\]](#)  
OR  
one of the following CPT codes:  
33660-33665 (atrioventricular valve repair)  
33400-33403 (aortic valve valvuloplasty)  
33420-33430 (mitral valve repair/valvuloplasty/replacement)  
33460 (valvectomy, tricuspid valve, with cardiopulmonary bypass)  
33463-33468 (tricuspid valve repair/valvuloplasty/replacement)  
33475 (replacement, pulmonary valve)

33496 (prosthetic valve dysfunction repair)  
0257T (implantation of catheter-delivered prosthetic aortic heart valve; open thoracic approach)  
0258T (transthoracic cardiac exposure for catheter-delivered aortic valve replacement; without cardiopulmonary bypass)  
0259T (transthoracic cardiac exposure for catheter-delivered aortic valve replacement; with cardiopulmonary bypass)  

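### Duration of AF, CHF and hypertension is counted from the earliest EMR record with no account of when that record begins, so the arm comparison mixes disease duration with record length

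*Combined protocol and SAP*

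**What the plan says.** Table 1 defines duration of AF as "Years/months prior to initiation of dabigatran/warfarin", so the target is time since onset or diagnosis. The value to be recorded is "Number of months prior to index date for the earliest note". CHF has the same rule. Hypertension has "Number of months prior to index date for the earliest date", and there the trigger may be a note, a systolic reading above 120 mmHg or a drug. All of these are secondary outcomes.

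On how far back the record must go, the readable text says little:

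- Section 9.3.2 has characteristics assessed up to and including the index date and gives no starting point.
- The abstract's inclusion list asks only for "Presence of electronic medical records (for the EMR-based subset".
- The one minimum history, in section 9.11.1, is "At least 12 months (365 days) continuous enrollment". It concerns insurance enrolment, not the EMR.

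Under Objective 1 in section 9.7.1, "the mean and standard deviation for continuous characteristics will be calculated" for each exposure group. The stated use is that "This analysis will aid in identifying EMR characteristics that are unbalanced across exposure groups", and such characteristics are then regarded as potential unmeasured confounders after matching.

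**The concern.** A note cannot be older than the record that holds it. For a chronic condition that was present before the EMR begins, months since the earliest note measures how long the patient has been in that EMR system, not how long the patient has been ill. Such a value does not look missing. It enters the mean as an ordinary number.

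The study exists to judge whether characteristics outside the claims data differ between dabigatran and warfarin initiators. If the recorded duration is partly record length, a small difference between arms does not show that durations are similar, and a large one does not show that they differ. Without the start date of each EMR, the report cannot tell these cases apart.

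**Working it through.** **The plan's own figures.** The documents give no figure for disease duration, EMR look-back or a duration difference of interest, so there is none to reproduce on this point. The subset size matters for the cost of the fix. Section 9.5 takes 5.5% of about 20,000 per arm: 20,000 × 0.055 = 1,100, as stated. The abstract's 15,000 per arm would give 15,000 × 0.055 = 825.

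**Model.** Let T be true duration, L the EMR look-back, and min(T, L) the recorded duration. This assumes that a condition already present is noted when the record opens. If T is exponential with mean m and L is uniform on 0 to c, independent of T, then

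E[min(T, L)] = m − (m²/c)(1 − e^(−c/m)).

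All values of m and c below are assumptions.

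**Equal look-back, true means 36 and 24 months (true difference 12).**

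| c (months) | m = 36 | m = 24 | Recorded difference | Share of 12 kept |
|---|---|---|---|---|
| 24 | 36 − 54 × 0.4866 = 9.72 | 24 − 24 × 0.6321 = 8.83 | 0.90 | 7% |
| 48 | 36 − 27 × 0.7364 = 16.12 | 24 − 12 × 0.8647 = 13.62 | 2.49 | 21% |
| 96 | 36 − 13.5 × 0.9305 = 23.44 | 24 − 6 × 0.9817 = 18.11 | 5.33 | 44% |

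**Sensitivity to the assumed inputs.**

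- For 36 vs 48 months, the same formula keeps 4% of the difference at a mean look-back of 12 months (c = 24) and 65% at 120 months (c = 240).
- For 12 vs 18 months, it keeps 44% at a mean look-back of 24 months and 75% at 60 months.
- With a fixed look-back c, the mean is m(1 − e^(−c/m)). For 60 vs 84 months and c = 6, the recorded difference is 0.08 of 24 months (under 1%). For 6 vs 9 months and c = 60, it is 2.99 of 3 months (about 100%).

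**Standardized mean difference (SMD).** These come from simulation with true means of 36 vs 48 months and a mean look-back of 24 months in both arms.

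- Exponential durations, uniform look-back: 0.28 becomes 0.12.
- Lognormal durations (log-SD 1.2), uniform look-back: 0.16 becomes 0.15.
- Lognormal durations, fixed look-back: 0.16 becomes 0.21.

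The difference in months shrinks in all three cases. The SMD need not.

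**Unequal look-back.**

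- No true difference (m = 36 in both arms), look-back uniform on 0–48 vs 0–72 (means 24 vs 36): 20.44 − 16.12 = 4.3 months recorded, with a simulated SMD of 0.29.
- True means 36 vs 48, with look-back means 36 vs 24: the formula gives 20.44 for the first arm and 48 − 48 × 0.6321 = 17.66 for the second. The recorded difference is −2.8 months against a true +12, so the sign is reversed.

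**What the proposed summary would return.** Among patients with L of at least 12 months, whether T exceeds 12 months can be read from the record under this model. For m = 36 and 24, the proportions are e^(−12/36) = 71.7% and e^(−12/24) = 60.7%. The 11.0-point difference is the same for all three values of c in the table.

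**The case against.** **The size is assumed.** The three look-back scenarios all start at zero, with means of only 12, 24 and 48 months, which favours heavy loss. If EMR histories are long relative to disease duration, little is lost. This stands. A reader might infer that real differences are largely erased, but the documents supply neither quantity that this would need, and the share kept ranges from under 1% to about 100%.

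**The direction is not fixed.** A reader might also infer that balance is overstated and confounding understated. The SMD can hold or rise, and unequal look-back can create an imbalance that is not there. Section 9.7.1 states no rule under which a characteristic would be declared balanced. This stands as well.

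**Importance.** It is tempting to say that the protocol names AF and CHF duration as poorly captured in claims. It does not. Section 7 gives body mass index, smoking, family history and alcohol as examples, and the abstract says only that some characteristics may be reflected differently. The durations are secondary, and Table 1 also gives each a present/absent indicator, so CHF and hypertension history are not compared through months alone.

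**Hypertension.** Its date can come from a blood pressure reading or a drug. The cap still applies, since no entry predates the record, but the simple min(T, L) model is not shown to fit.

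**Existing safeguards.** Matching on calendar quarter makes similar look-back plausible but does not ensure it in the linked subset, and it does not prevent shrinkage. Table 8 and the check in section 9.11.2 use claims covariates and the propensity score, not EMR depth. The missing-data review (section 9.7.1) and the limitations (section 9.9) do not mention truncated history. None of these resolves the point.

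**Unreadable text.** Sections 9.3.3 and 9.6, parts of 9.7.1 and Figure 1 cannot be read in this copy. A look-back rule may be there.

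**Conclusion.** The point holds in a limited form. As written in the readable plan, the duration variables are capped at EMR look-back, and nothing collected separates the two. The size of a recorded arm difference, and possibly its sign, therefore cannot be read as a difference in disease duration.

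Under similar look-back, the difference in months shrinks: 12 months becomes about 0.9, 2.5 or 5.3 in the scenarios shown. Those figures rest on exponential durations, uniform look-back independent of duration, and prompt noting of existing disease. None of these can be checked from the documents. No general statement about how much is lost, or about which way the balance assessment is biased, is supported.

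This is a worthwhile improvement to secondary descriptive outcomes. It does not threaten the study's main comparisons.

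**What to change.** 1. Extract each linked patient's first EMR activity date and report look-back to index by arm (median, quartiles, and the share with at least 12 months).
2. Compare duration as the proportion over 12 months among patients with at least 12 months of EMR before index, alongside or in place of raw means. Alternatively, treat a condition already noted at EMR entry as censored at the look-back and use Kaplan–Meier summaries. That route assumes look-back is unrelated to duration, and medians may not be reached if look-back is short.
3. State whether an onset date written inside a note overrides the date of the note.
4. Specify all this before the data vendor runs the EMR balance analysis described in section 9.11.2, and confirm that the vendor can supply the date. The documents do not show that it is available.

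The cost is one date per patient and some precision. If look-back were uniform on 0–24 months, half of 1,100 per arm, or 550, would qualify. For a proportion near 50%, the 95% half-width for the arm difference would rise from 1.96 × √(0.5/1,100) = 4.2 points to 1.96 × √(0.5/550) = 5.9 points. For CHF, only patients with the condition contribute, so intervals would be wider. The restricted result describes patients with at least a year of EMR, and extending it to the whole linked subset again assumes that look-back is unrelated to duration.
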